### **Statistical Analysis Plan**

IBM SPSS Statistics version 24 was used to complete all quantitative data analyses. Frequencies were used to examine feasibility, including recruitment and eligibility rates, rates of attendance at each session and assessment appointment, and satisfaction with the intervention. Paired *t* tests were conducted to examine pre-post differences in the health outcomes of interest and Cohen's *d* effect sizes and confidence intervals were calculated to examine the effect size of any changes in BMI, mindfulness, emotion regulation, eating behaviors, quality of life, impulsivity, and blood pressure. For participants who did not complete post-assessment (*n* = 3), we used a last observation carried forward imputation.

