## Study Protocol

**Study Setting.** This study took place at a multidisciplinary, research-oriented weight management clinic located within a large children's hospital in the Mid-Atlantic during February through August of 2019. This clinic accepts patients with obesity aged 6 months to 21 years. Approximately 100 new patients are seen annually. Approximately 39% of the patients seen are Black or African Americans, 28% are Hispanic American and 20% are White Americans. 65% of the patients have Medicaid and 34% are private or commercially insured. The clinic follows the recommended standard of medical management of overweight and obesity. The clinic team conducts a comprehensive evaluation to assess dietary and activity behavior change needs of each patient and family, as well as obesity-associated comorbidities. In addition to management of comorbidities, goals for improved physical activity and dietary behaviors are set with the patient and family at each visit.

**Inclusion and exclusion.** Adolescents were eligible if they were between the ages of 12 – 17, a current patient of the affiliated obesity clinic, and had a BMI greater than 30 kg/m^2. Adolescents were ineligible if they had a known genetic cause of obesity, had been diagnosed with a severe intellectual or learning disability, had been diagnosed with an autism spectrum disorder or current psychosis, or were currently in psychotherapy. These exclusion criteria were selected because they might influence the degree to which an adolescent responds to behavioral weight loss and/or their ability to actively take part in a standard mindfulness intervention.

**Recruitment.** Medical providers and other clinic staff were informed about the study and referred interested patients' parents/caregivers to the research team. Interested patients were screened for eligibility and eligible patients were consented in the presence of a parent/caregiver and scheduled to complete a baseline assessment.

**Participant assessment schedule and measures.** Participants completed a series of assessments within a private clinic room at the obesity clinic. These measures were completed at baseline and post-intervention, unless otherwise stated.

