### ***Feasibility outcomes.***

*Assessing recruitment feasibility.* Recruitment feasibility was examined through research staffs' detailed tracking of recruitment processes (e.g., referrals from physicians, patients approached in the waiting room), the number of interested patients, and the number of patients eligible after the initial screening. We documented all cases of ineligibility and the reason for disqualification.

*Assessing retention feasibility.* Retention feasibility was tracked via attendance; research staff took attendance during each assessment period and intervention session. Any enrolled participants who dropped out (defined as participants who either explicitly stated that they would like to leave the program or who missed two consecutive sessions in a row without contacting the research team) were contacted by phone to inquire about their reasons for ending the program, as a method of assessing any barriers to intervention completion.

*Assessing participant satisfaction.* We assessed participants' satisfaction with the mindfulness intervention by having them complete a satisfaction survey at the end of the intervention. This survey evaluated: 1) reactions to the topics discussed and skills reviewed; 2) comfort with facilitators; 3) opinions of the materials used; and 4) overall satisfaction with the intervention at that point in time. Ten of these items were scored on a Likert-scale of 1 (strongly disagree) to 5 (strongly agree) (e.g., "Participating in this program helped me to better manage my eating habits") and eight of these items invited open-ended responses (e.g., "What were the challenges of participating in this study?"). Participants were also asked to report their favorite and least

favorite components at the end of each session. This feedback will inform potential adaptations made to the intervention prior to a larger randomized controlled trial (RCT).

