### **Participant self-report measures.**

*Demographic questionnaire.* Assesses age, gender, and race/ethnicity. This measure was only completed at baseline assessment.

*Mindful Attention Awareness Scale-Adolescent (MAAS-A).* The MAAS-A is a 15-item measure of dispositional mindfulness. Participants rated how frequently they experience episodes of mindless behavior (e.g., “I find myself doing things without paying attention.”) on a scale of 1 (almost always) to 6 (almost never). This measure has established psychometric properties in diverse adolescent samples.

*Eating Disorders Examination-Questionnaire (EDEQ).* Participants reported instances of overeating, loss of control eating, and binge eating over the last four weeks via 3 items of the EDEQ. This measure was selected to examine potential changes from baseline to post-assessment in eating behaviors that are associated with emotion regulation and risk for obesity that might be influenced by mindfulness training. The EDEQ yields reliable and valid scores. Adolescent responses to the EDEQ correspond strongly with clinical interviews assessing disordered eating.

*Difficulties in Emotion Regulation Scale – Short Form (DERS – SF).* The DERS-SF is an 18-item, widely used self-report measure of emotion regulation problems that has been validated in adolescent samples. This measure was selected to examine potential changes from baseline to post-assessment in emotion regulation, which is theorized to be a key driver of disordered eating (e.g., binge eating, overeating) in adolescents with obesity.

*Youth Quality of Life Instrument – Short Form (YQOL-SF).* The 15-item YQOL-SF measures generic quality of life in youth with and without chronic conditions, ages 11-18 years. It has established psychometric properties in adolescent samples.

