**Facilitators and Training.** The mindfulness components of the intervention were facilitated by two interventionists with established mindfulness practices, including one graduate-level clinical psychology student and one first-year medical student. Each facilitator received extensive supervision from the first and second authors (both licensed clinical psychologists) via weekly meetings. Participants met with the same facilitator throughout the course of the intervention. The usual care components were facilitated by medical providers within the obesity clinic.

**Adequacy of Sample Size.** Our study's primary aim was to examine feasibility and refine aspects of the research approach; therefore, a formal sample size calculation was not warranted. Given budgetary and logistical constraints, our aim was to recruit 15 adolescents over a six-month period through a single clinic site, which is sufficient to provide useful information about the feasibility of the protocol.

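### With only baseline and post-intervention assessments, last observation carried forward enters a change of exactly zero for 3 participants, and no analysis described tests that assumption

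*Combined protocol and SAP*

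**What the plan says.** The Study Protocol, under the participant assessment schedule, sets two time points: "These measures were completed at baseline and post-intervention, unless otherwise stated". The exceptions it states do not add a time point for any health outcome:

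- Demographic questionnaire: "This measure was only completed at baseline assessment".
- Satisfaction: participants were to "complete a satisfaction survey at the end of the intervention", and gave feedback on the components after each session.
- Attendance was tracked at every session, but it is a feasibility measure.

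The sections on self-report measures, the Go/No-Go task, anthropometrics and blood pressure mention no interim measurement.

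The Statistical Analysis Plan uses paired t tests for the health outcomes and adds a standardised measure, Cohen's d. Of this it says: "effect sizes and confidence intervals were calculated to examine the effect size of any changes". Seven outcomes are covered: blood pressure, BMI, quality of life, mindfulness, impulsivity, eating behaviors and emotion regulation. For the 3 participants with no post-assessment, "we used a last observation carried forward imputation". It does not say that this amounts to assuming no change. It describes no analysis of observed pairs and no sensitivity analysis.

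On numbers, Adequacy of Sample Size says "our aim was to recruit 15 adolescents over a six-month period through a single clinic site". The number actually enrolled is not given.

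**The concern.** Carrying the last observation forward is usually understood to use a later, partial follow-up value. Here there is no such value, so the rule sets post equal to baseline and the change to zero on every health outcome. Three zeros then enter a small paired sample with the same standing as measured changes.

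This moves the quantities the plan uses to describe the health outcomes, namely the mean change, d and its interval. From the analysis described, a reader cannot tell how much of a small d comes from the three zeros, or how much smaller it would be if the non-completers did worse than no change. With no formal sample size calculation, the effect sizes and intervals carry most of the exploratory information on these outcomes.

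**Working it through.** The plan states no effect size, so there is no figure to reproduce. The check compares the rule with the observed-pairs analysis.

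**Inputs**
- Participants filled in: 3 (Statistical Analysis Plan).
- Total analysed, N: not stated. Assumed 10, 15 (the recruitment target) and 20. Observed pairs n = N − 3.
- Observed d: not stated. Assumed 0.50 and 0.80. Changes are scaled so that the observed pairs have mean d and SD 1, and positive means improvement.
- Denominator of d: not stated. The SD of change is assumed.

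**Step 1: mean change.** Mean = d × n/N, so the multiplier is 7/10 = 0.70, 12/15 = 0.80 or 17/20 = 0.85.

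**Step 2: d.** The SD after filling in is √{[(n − 1) + (3n/N)d²]/(N − 1)}.
- N = 15, d = 0.50: SD = √[(11 + 2.4 × 0.25)/14] = 0.910, and d = 0.40/0.910 = 0.44.
- N = 15, d = 0.80: SD = √[(11 + 2.4 × 0.64)/14] = 0.946, and d = 0.64/0.946 = 0.68.

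The ratio to the observed d is at most (n/N)√[(N − 1)/(n − 1)], which is 0.857, 0.903 and 0.926 at N = 10, 15 and 20. So d on the SD of change always falls, by at least about 14%, 10% and 7%.

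| N | observed 0.50 becomes | observed 0.80 becomes |
|---|---|---|
| 10 | 0.41 | 0.62 |
| 15 | 0.44 | 0.68 |
| 20 | 0.45 | 0.71 |

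**Step 3: the interval.** The effect depends on what the interval is for.

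*Mean change.* At observed d = 0.50 the t-interval half-width falls from 0.925 to 0.609 (N = 10, ×0.66), from 0.635 to 0.504 (N = 15, ×0.79) and from 0.514 to 0.438 (N = 20, ×0.85). Simulated coverage at N = 15, with normal changes and dropout completely at random, is about 93%, 91% and 89% for true d of 0.5, 0.8 and 1.0. At N = 15 the narrowing reverses only above an observed d of about 1.76.

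*Cohen's d (noncentral t).* At N = 15, 0.50 (−0.11 to 1.09) becomes 0.44 (−0.10 to 0.96). Coverage in the same three cases is about 95.5%, 94.9% and 93.5%, which is near nominal.

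**Step 4: p values.** At N = 15, observed pairs and the filled-in analysis both give p = 0.111 at observed d = 0.50. At 0.80 they give 0.018 and 0.020.

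**Step 5: if the 3 worsened.** With fill value f, mean = (nd + 3f)/N and the sum of squares is (n − 1) + n(d − mean)² + 3(f − mean)². For N = 15, d = 0.80 and f = −0.5, the mean is (9.6 − 1.5)/15 = 0.54, the sum of squares is 11 + 12(0.26)² + 3(1.04)² = 15.06, the SD is √(15.06/14) = 1.037 and d = 0.52.

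| Fill for the 3 (N = 15, observed d = 0.80) | d (95% CI) | p |
|---|---|---|
| 0 (the plan's rule) | 0.68 (0.10 to 1.23) | 0.020 |
| 0.25 SD worse | 0.60 (0.04 to 1.14) | 0.036 |
| 0.5 SD worse | 0.52 (−0.03 to 1.05) | 0.063 |

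For observed d = 0.50 the corresponding values of d are 0.44, 0.37 and 0.31.

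**The case against.** The plan names the method, says whom it applies to and gives the number. A reader who sets that beside the two-point schedule can work out the zero change. That stands, and it makes the labelling a reporting point. What remains is that nothing described tests the assumption.

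Feasibility is the primary aim and is analysed by frequencies, which the rule does not touch. No decision rule in the documents depends on d, and p values hardly move. All of that stands and limits the weight of the point.

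The strongest objection concerns precision. A reader might infer that the rule makes every reported interval falsely precise and that observed pairs would simply be better. The documents do not support that. The text places the intervals directly after Cohen's d, so they may well be intervals for d, and their coverage is near nominal. With random dropout at N = 15, the filled-in d also has a smaller root mean squared error than the uncorrected observed-pairs d: 0.27 against 0.35, 0.28 against 0.38 and 0.29 against 0.42 at true d of 0.5, 0.8 and 1.0. Part of the reason is that d from 12 pairs is biased upward by about 7%. For the mean change at d = 0.5 the errors are 0.25 against 0.29, again in favour of the filled-in analysis. The charge of false precision therefore applies only if the interval is for the mean change.

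A reader might also infer that the rule is conservative, or that the 3 did worsen. Neither follows. The shrinkage is relative to observed pairs, not to the truth, and the documents say nothing about how these 3 fared. Dropouts "were contacted by phone to inquire about their reasons for ending the program", but the text does not say that reasons were obtained from these participants.

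Finally, the plan cites two references for the effect sizes, and these may define the denominator and the interval. They cannot be seen here, so the unnamed denominator is an optional clarification.

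**Conclusion.** The point holds and is minor. On the schedule given, the rule is baseline carried forward and enters exactly zero change for 3 participants. Relative to observed pairs, it multiplies the mean change by (N − 3)/N and always lowers d on the SD of change. An interval for the mean change is too narrow over the plausible range of effects. If the interval is for d, what is left is an untested assumption, which matters because the filled-in result lies between observed pairs and any case in which the 3 worsened. In the example worked, moving from zero change to 0.5 SD worse takes the lower limit for d below zero.

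The conclusion assumes that none of the 3 had a partial post-assessment and that no other clinic measurement was carried forward; the documents describe neither. The sizes depend on the assumed N and d, and the coverage and error figures on normal changes with random dropout. They illustrate the effect and do not measure what happened in this trial.

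**What to change.** Keep the present result and identify it as baseline carried forward, assuming zero change for 3 participants. Beside it, report:

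1. the observed-pairs mean change, d and confidence interval, with the number of pairs for each outcome;
2. one sensitivity run in which the 3 non-completers worsen by a stated amount, for example 0.25 and 0.5 SD of change.

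Two further additions are optional: name the denominator of d and say whether the interval is for d or for the mean change; and give the reasons for dropout where they were obtained.

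The cost is a few lines of text, the same tests rerun without three rows, and one fill-in run. The study is already described as done, so these are additions to the reporting and should be presented as such. The downside is that observed-pairs intervals are wider, and observed pairs are themselves biased if dropout is related to outcome. For that reason both results should be shown and neither replaced.

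### Carrying baseline forward sets BMI and blood pressure change to exactly zero for the 3 participants without a post-assessment, and the plan does not say whether clinic readings were sought

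*Combined protocol and SAP*

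**What the plan says.** The Statistical Analysis Plan compares baseline with post-intervention values: "Paired *t* tests were conducted to examine pre-post differences in the health outcomes of interest". Cohen's d and confidence intervals are added for "changes in BMI, mindfulness, emotion regulation, eating behaviors, quality of life, impulsivity, and blood pressure". For the 3 participants without a post-assessment, "we used a last observation carried forward imputation". No outcome is exempt, and no sensitivity analysis is described.

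The Study Protocol, under the assessment schedule, gives two time points: "These measures were completed at baseline and post-intervention, unless otherwise stated". 

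Three statements bear on whether another source of data might exist. To be eligible, an adolescent had to be "a current patient of the affiliated obesity clinic". The Study Setting paragraph says of the clinic that "goals for improved physical activity and dietary behaviors are set with the patient and family at each visit". Under Facilitators and Training: "The usual care components were facilitated by medical providers within the obesity clinic". Study assessments also took place in a room at that clinic.

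**The concern.** With two time points, the last observation before a missed post-assessment is the baseline. The rule therefore assumes that BMI and blood pressure did not move at all in these 3 adolescents. This does two things. It replaces their true change, whatever it was, with zero. It also adds identical values to the set of differences, which shrinks the SD of change while the sample size is counted in full, so the interval is too short.

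For the questionnaires and the Go/No-Go Task, a missed session leaves no evident substitute. Height, weight and blood pressure are different, because a weight management clinic that is also treating the patient may have recorded them. The plan does not mention looking.

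At stake are the effect sizes and intervals for BMI and blood pressure. The protocol looks ahead to a larger randomized trial, and an SD of change that is too small could carry over into its planning.

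**Working it through.** The documents give no sample size calculation, SD or result for these outcomes, so there is no figure of the plan's own to reproduce. The check is algebra on a paired design.

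**Inputs**
- Missing post-assessments: m = 3 (Statistical Analysis Plan).
- Enrolled: N = 15 is assumed. It is the recruitment aim under Adequacy of Sample Size; the number enrolled is not stated. Range tried: 10 to 20.
- Completers: c = N − 3, with mean change D and SD of change s = 1. D from 0 to 0.8 SD is assumed.
- For comparison, N real pairs are taken to have the same SD of 1.

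**Share of pairs set to zero**
- 3/15 = 20%; 3/10 = 30%; 3/20 = 15%.

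**Mean and SD of change under the rule**
- Mean = D × c/N.
- Variance = [(c − 1)s² + cD² − N(Dc/N)²]/(N − 1).
- N = 15, D = 0: mean 0; SD = √(11/14) = 0.886.
- N = 15, D = 0.5: mean = 0.5 × 12/15 = 0.40; variance = (11 + 3 − 2.4)/14 = 0.829; SD = 0.910. Standardized by the SD of change, the effect is 0.40/0.910 = 0.44, against 0.50 in completers.

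**95% half-width = t(0.975, n − 1) × SD/√n, where n is the number of pairs**
- 12 completers only: t(11)/√12 = 0.635.
- 15 real pairs: t(14)/√15 = 0.554.
- Rule, D = 0: 0.554 × 0.886 = 0.491, which is 11% below 0.554 and 23% below 0.635.
- Rule, D = 0.5: 0.554 × 0.910 = 0.504, which is 9% below 0.554 and 21% below 0.635.
- Over N = 10 to 20 and D = 0 to 0.8, the interval is 4% to 18% narrower than with N real pairs and 12% to 37% narrower than for completers only.

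**Error in the mean = (3/15) × the true mean change in the 3**

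The changes below are illustrations, not data. Suppose the 12 completers lost 0.3 kg/m² on average. The rule gives (12 × −0.3)/15 = −0.24.
- If the 3 gained 0.5: (−3.6 + 1.5)/15 = −0.14. If they gained 1.0: (−3.6 + 3.0)/15 = −0.04. The rule overstates the loss.
- If the 3 lost 0.5: (−3.6 − 1.5)/15 = −0.34. If they lost 1.0: (−3.6 − 3.0)/15 = −0.44. The rule understates it.
- A 5 mmHg change in the 3 moves the mean blood pressure change by 3 × 5/15 = 1 mmHg.

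**The case against.** The strongest reply is that the alternative data source is not established. Being a current patient is a condition at entry, not evidence of later attendance. The protocol gives no visit interval and does not say that weight, height or blood pressure is recorded at follow-up visits. It does not show that the 3 stayed in care. Chart permission cannot be checked from the text available. All of this stands. A reader might infer that routine visits should have supplied real values, or that the study discarded measurements it had. The documents support neither; they support only that such readings may exist and that the plan is silent about them.

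Other parts of the reply also stand:
- A reader might treat BMI and blood pressure as the only objectively measured outcomes. They are not: the Go/No-Go Task is a computerized performance test.
- A wide window around the planned date would do harm. Four weeks either side would reach well back into a 6-week intervention, and an early reading used as a post value would itself pull the change towards zero.
- Clinic readings may not follow the study's procedures for clothing, shoes, scale and seated rest.
- The study is reported as finished, with the 3 already known, so a change now cannot count as prespecified.

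What the reply does not remove is the effect of the rule itself. A reader might defend carrying baseline forward as conservative. It is not reliably so, since any worsening in the 3 is recorded as no change and the interval is shortened whichever way they moved.

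**Conclusion.** The point holds, at minor severity. The zero change for the 3 participants follows directly from the schedule and the rule. With N = 15, one pair in five is a fixed zero, and the interval is about 9% to 11% too narrow against 15 real pairs, for a completer change between 0.5 SD and 0. These figures rest on the assumed enrolment and on real pairs having the completers' SD. The direction of the error in the mean is unknown, because nothing is reported about how the 3 fared; a reader should not infer that the rule flatters the intervention.

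That clinic readings could replace the zeros is plausible from eligibility, usual care and the shared site, but unconfirmed. The consequence is confined to exploratory, uncontrolled health outcomes in a study whose primary aim is feasibility.

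**What to change.** For BMI and blood pressure only:

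1. State whether clinic-recorded height, weight and blood pressure were sought for the 3 participants.
2. Where the study post-assessment is missing and chart use is permitted, use the clinic value closest to the planned post date, within a narrow window that opens no earlier than the end of the 6-week intervention. Fix the window before looking at the values.
3. Flag each such value as clinic-sourced and report how many values came from the study, the clinic and imputation.
4. Where no such value exists, show the completers-only estimate and interval beside the imputed one, so that the too-narrow interval does not stand alone.
5. Since the study is complete, label the added analysis as post hoc.

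The cost is a few sentences in the plan, three chart look-ups and a check that the authorisation covers them. The downside is that clinic readings may differ in date and conditions from those described under the anthropometric and blood pressure measures; the source flag lets a reader judge this. The questionnaires and the Go/No-Go Task gain nothing from chart data, so this change does not touch them.
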